12.4 Final Analysis Plan

The usual inspection for outliers and influential data points will be conducted along with summary statistics and evaluations of distributions of the data. We have experience with the clinical outcome measures, which have approximately normal distributions. In the case of non-normal data, we will use standard transformations (e.g., log) or explore alternatives (e.g., non-parametric approaches or other distributions such as Poisson).

Period 1: parallel arm phase: Standard approaches for a parallel 2-arm randomized study will be conducted for the first period of the sequence, across all buildings. This analysis allows direct comparison of the AMI vs. the Campaign approach for clinical outcomes (Study Hypothesis #1).

Periods 1 and 2: assessing sequence of interventions: Study Hypothesis #2, which sequence gives better clinical outcomes, will be addressed using repeated measures models. Depending on whether the outcome is continuous or dichotomous, we use general linear mixed models (GLMM) or general estimating equations (GEE), respectively, to fit a model with intervention and period effects using the MIXED procedure in SAS®. Each set of measures from the same person (e.g., gingival outcomes) are treated as a correlated cluster of data. An AR-1 correlation structure is

likely to be appropriate. Customized contrasts can be constructed to make comparisons

between time points. Time-varying covariates can be used in these models, and some missing data (under MAR or MCAR assumptions where applicable), is allowable.

Baseline & health status variables: As this study randomizes at the level of site and individuals are not randomized, we will likely stratify some results (or adjust in models) for demographics such as age, gender, marital status and individual characteristics such as health status, ADLs, depressive symptoms (CES-D) and oral health status (self-assessment). Any variable that shows potential for confounding or effect modification will be accounted for appropriately in all stages of the analysis.

Intervention variables: As all subjects are exposed to the same interventions, it is of interest to unpack the intervention into 1) dosage (percent of talking points covered for all focal points (domains) addressed in the intervention, and 2) exposure to focal point messages during campaigns. Study Hypothesis #5, regarding dosage of interventions, will be assessed by creating an ordinal scale that measures an individual's exposure to talking points through participation in the AMI and exposure to messages via campaigns, thus creating a measure of dosage. We will then assess if dosage predicts better outcomes. This can be done directly (e.g., compare mean gingival scores across dosage levels with ANOVA) or dosage can be used as a predictor variable in the statistical models and causal pathway analyses. Oral health skills/Practice-to-Mastery (a 4 point Likert scale) and focal points (count variable) can be analyzed using similar techniques and approaches.

MFFD layout: N at the beginning of study			
	Sequence	N	
Building 1	A:B	60	
Building 2	B:A	60	
Building 3	A:B	60	
Building 4	B:A	60	
Building 5	A:B	60	
Building 6	B:A	60	

Secondary Outcome of General Oral Health Assessment Inventory (GOHAI): We will conduct a set of secondary analyses with GOHAI as a continuous outcome. It will also be incorporated into our statistical/mediator models as predictor to see if it acts as an effect modifier.

Cognitive Mediators: The following variables will be incorporated into the causal pathway analysis to address example hypotheses #3 and #4: knowledge, oral health beliefs/norms, social support, oral hygiene behaviors, fears/worries, practice to mastery, and behavioral intentions. We will use longitudinal mediation to compared the efficacy of AMI-PM+CA+PM to CA+PM+AMI-PM in terms of whether they differ significantly in the amount of change that they engender in the gingival index and plaque score, indirectly through the mediators measured in our model.

outcomes.

The classical Barron & Kenny (1986) mediation approach to longitudinal mediation would examine whether the intervention impacts the levels of our mediators, such as beliefs, at T1 (for example), which in turn affect clinical outcome measures resulting from participant behaviors as measured by the Gingival index and Plaque Scores at T2. Or, simply put, whether levels of self-efficacy at T1 are associated with the levels of gingival index scores at T2 indirectly through self-efficacy at T1 (and other mediators previously referenced). But, we are interested in examining whether there is a change in our mediators over time, and if so, whether this change significantly leads to a change in behaviors, as assessed by the Gingival Index and Plaque Scores. Recent methodological studies actually show that the analysis of change is more appropriately captured by specifying change (differences) in self-efficacy and our other mediators and behavioral outcomes between adjacent time points (i.e. T1-T0, and T2-T1) as latent difference scores, and explicitly modeling these change scores to represent dynamic change, i.e., the impact of change in the mediators on change in the behavioral

Hypothesis #3 will be tested using latent change score analysis specifying AMI and Campaign as predictors of change in behavioral beliefs(ΔBB), OH social support (ΔSS), locus of control beliefs(ΔCB), self-efficacy(ΔSE), fears/worries ($\Delta F/W$), social norms (ΔSN), and behavioral intentions (ΔSI) from baseline to first and second follow-up.

To test hypothesis #4, we will conduct dynamic mediation using latent change (difference) score (LCS) mediation analysis. The analyses will be conducted in Mplus 7 where change (difference) scores representing differences in each mediator and outcome variable from baseline to final follow up (i.e. T1-T0 (ΔT_{10}), and T2-T1(ΔT_{21}) will be generated. It is the difference scores of the mediators and outcome variables that are modeled. Generally speaking, causal paths specifying latent (true) change, represented by change in knowledge, oral health beliefs/norms, OH social support, oral hygiene behaviors, fears/worries, oral health practice to mastery skills, and behavioral intentions in going from T0 to T1, and T1 to T2 will be specified, to predict change in Gingival Index and Plaque Scores at T2 (i.e., ΔGingival Index₂₁, ΔPlaque score₂₁). For example, we will test whether change in fears/worries from T0 to T1 significantly predicts changes in Gingival Index and Plague Scores at final follow-up, T2 (ΔGingival Index₂₁, Δ Plague scores₂₁). To assess the impact of the change in self-efficacy (Δ SE). on changes in Gingival Index scores (ΔGingival Index), direct and indirect paths from change in self-efficacy from baseline to first follow up (ΔSE₁₀) that predict the change in Gingival Index at the final follow-up (ΔGingival Index₃₀) will be specified and tested. Select direct and indirect paths from change scores of the other mediator variables to change scores of behavioral outcomes will also be specified in a similar fashion, and all these relationships will be tested simultaneously.

Summary: Using a conservative set of assumptions and based on our own pilot data, we have demonstrated, using our pilot data estimates, that we will have sufficient power to detect significant changes, using a two-group t-test which makes minimal

IRB Review
IRB NUMBER: 14-188-6
IRB APPROVAL DATE: 01/03/2019
12/14/2018

Good Oral Health: A Bi-level Intervention to Improve Older Adult Oral Health Protocol #14-046-E

assumptions about the data. It is worth noting that the proposed statistical models have greater power characteristics than the t-tests used to calculate power.

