4 STUDY DESIGN

Overall Design: The study utilizes a modified fractional factorial design (MFFD) which compares the short term outcomes of the two intervention components: the tailored individual level brief intervention (AMI-PM) and the group level Campaign including embedded oral health skills development through practice-to-mastery (CA+PM). It also evaluates the effects of differential sequencing of these modes of delivery components in relation to short and longer term outcomes. Finally, it evaluates intervention mechanisms through mediational modeling of the cognitive and the behavioral components over time. The two intervention components are the individualized AMI-PM (Component A), and the group CA+PM (Component B). To evaluate sequencing we will randomize pairs of senior residences into two conditions: Condition 1 and Condition 2. Buildings in Condition 1 will initiate with Component A, followed by Component B. Buildings in Condition 2 will initiate with Component B, followed by Component A. This study design will allow us to compare the AMI-PM outcomes to CA+PM short term outcomes, and to determine which condition sequence (A+B or B+A) will produce the best clinical outcomes. Each of 3 cycles of Condition 1 (A+B) compared to Condition 2 (B+A) will take place over a 16-18 month period each in two matched buildings with an N of 60 per building (N per cycle of 120; total N for all three cycles approximately 360). We anticipate an attrition rate of approximately 25% and a final N of approximately 270 by the T3 measure, 135 in Condition 1 and 135 in Condition 2. Primary outcomes are improvements in gingival health and decreases in plaque scores.

A description of the study population: Participants will be recruited from low income senior housing in Central Connecticut. The population consists of independent living older adults many of whom have chronic health conditions. Residents also include adults less than 62 years of age residing in these buildings who are disabled. Residents must meet income guidelines and be over the age of 62 or be disabled children and adults between the ages of 18 and 61.

Methods for collecting data for assessment of study objectives: Data collection will consist of clinical assessment, and surveys evaluating changes in cognitive domains (See Section 16).

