5 STUDY ENROLLMENT AND WITHDRAWAL

The Pro-GOH target population consists of residents living in buildings housing older adults and disabled adults in Central Connecticut, including the towns of Hartford, New Britain, and Meriden. Based on previous studies in these buildings, we anticipate that the population in the study buildings overall will consist of approximately 40% African American/Caribbean, 45% Latino (mainly Puerto Rican) and 10-15% other ethnic (Euro-American and Polish) residents. Approximately 13% will be under 62 years of age and will have some form of disability. All buildings are located in low income or working class neighborhoods that are medically and socially disadvantaged. Residents often lack access to regular health care and are at high risk for a variety of health and mental health problems.

We will select, match and work in three pairs of buildings of 100 - 250 apartments each. Six buildings have agreed to participate (See letters of support). Our goal in selection of buildings is to achieve a representative sample of residents that approximate the ethnic/racial balance identified above. One building in each pair will be randomly assigned to each condition.

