5.4.1 Randomization Procedures

Buildings will be paired on the basis of their age, ethnicity and gender characteristics and randomized by a statistician. Individual participants will not be randomized.

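### Section 12.4 does not say how randomising six paired buildings enters the tests of Hypotheses 1 and 2; an unmatched person-level comparison at one visit would have a true size of about 10% to 18%, not 5%

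*Combined protocol and SAP*

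**What the plan says.** - **Allocation.** Section 5.4.1: "Buildings will be paired on the basis of their age, ethnicity and gender characteristics and randomized by a statistician". Section 5: "One building in each pair will be randomly assigned to each condition". Section 12.2 gives three buildings per sequence and 60 people per building. Section 4 expects "a final N of approximately 270 by the T3 measure, 135 in Condition 1 and 135 in Condition 2", which is 45 per building.
- **Hypothesis 1 (T1).** Section 12.4: "Standard approaches for a parallel 2-arm randomized study will be conducted for the first period of the sequence, across all buildings". The method is not named.
- **Hypothesis 2 (T2 and T3).** Section 12.4 will "fit a model with intervention and period effects using the MIXED procedure". On correlation it says: "Each set of measures from the same person (e.g., gingival outcomes) are treated as a correlated cluster of data". It adds: "Customized contrasts can be constructed to make comparisons" between time points.
- **Site randomisation.** Section 12.4 raises it once: "As this study randomizes at the level of site and individuals are not randomized". The consequence drawn is probable stratification or adjustment for individual characteristics such as age, gender and health status.
- **Clustering elsewhere.** Section 12.2 lowers the planning N from 135 to 123 per group for an ICC of 0.01 or 0.02. Section 3.2.4 lists building among the demographic moderators.

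For neither hypothesis does the text name a random building effect, a test on building means, a pair term, a cluster-robust variance or small-sample degrees of freedom.

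**The concern.** The comparison of conditions is a comparison of three buildings with three buildings. A person-level test omits building-to-building variation from the standard error of that comparison. It also takes its degrees of freedom from about 270 people instead of six buildings. Hypothesis 1, and the T2 and T3 sequence comparisons in Hypothesis 2, could then reach significance on building differences alone. Shared building effects are plausible here because one component is a campaign delivered to the whole building.

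The ICC allowance in Section 12.2 does not repair this. It changes how many people are planned for, but not the standard error or degrees of freedom of the test that is eventually run. Listing building as a moderator does not repair it either: building is nested in condition, so a fixed building effect cannot support a between-condition test.

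**Working it through.** **Inputs.** Two-sided alpha 0.05; 3 versus 3 buildings; m = 45 per building at the end of the study and at most 60 at T1; ICC 0.01 or 0.02 (Sections 4 and 12.2). Values marked as assumptions are not in the documents.

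**1. The plan's own figure.** The documents give power but no type I error for the clustered comparison. For the lowest row of the Section 12.2 table (plaque, difference 0.20, SD 0.47, 123 per group), the noncentrality is (0.20/0.47) × √(123/2) = 3.34. Power is 91.4%, against the stated 91. This is a person-level calculation.

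**2. Size of a person-level test at one visit, pairing ignored.** Design effect DE = 1 + (m − 1) × ICC; true size = 2 × [1 − Φ(1.96/√DE)].

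| m | ICC | DE | True size |
|---|---|---|---|
| 45 | 0.01 | 1.44 | 10.2% |
| 45 | 0.02 | 1.88 | 15.3% |
| 60 | 0.01 | 1.59 | 12.0% |
| 60 | 0.02 | 2.18 | 18.4% |

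Simulation at m = 45 (100,000 trials per setting) gave 10.3% and 15.3%. A t-test on the six building means (4 df) gave 5.0% at both ICCs.

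**3. Effect of pairing.** Suppose pairing absorbs a share f of the between-building variance (assumption). Then DE = 1 + ICC × [(1 − f)m − 1].

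- f = 0.5, m = 45: DE 1.215 and 1.43; size 7.5% and 10.1%.
- f = 0.5, m = 60: DE 1.29 and 1.58; size 8.4% and 11.9%.
- f = 1: DE 0.99 and 0.98; size about 5%.

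In simulation with f = 0.5 and m = 45, the unpaired six-mean test gave 3.9% and 3.6%, and the paired test (2 df) gave 5.1% and 5.0%.

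**4. Change from T0 in Hypothesis 2 (T2 − T0, m = 45).** Let rb be the correlation of building effects between visits (assumption) and rw the within-person correlation. With AR-1 of 0.5 (assumption) at lag 2, rw = 0.25. The ICC of change is ICC(1 − rb) / [ICC(1 − rb) + (1 − ICC)(1 − rw)].

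| rb | Size, ICC 0.01 | Size, ICC 0.02 |
|---|---|---|
| 1 (stable) | 5.0% | 5.0% |
| 0.8 | 6.4% | 7.8% |
| 0.5 | 8.5% | 12.0% |
| 0 (visit-specific) | 12% | 18% |

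Example, rb = 0.5 and ICC 0.01: 0.005/(0.005 + 0.7425) = 0.00669; DE = 1 + 44 × 0.00669 = 1.294; size 8.5%.

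**5. Power of a building-level test (4 df, m = 45), table values at face value.** The variance of a building mean is SD² × [ICC + (1 − ICC)/m], and the standard error of the difference is √(2 × variance/3).

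- Plaque 0.20/0.47: SE 0.0686 and 0.0784; noncentrality 2.91 and 2.55; power 60% and 49%.
- Gingival 0.50/0.81: SE 0.1183 and 0.1352; noncentrality 4.23 and 3.70; power 88% and 79%.
- Paired test (2 df), plaque, if matching removes no variance: 37% and 31%.

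**The case against.** **The plan does not state a wrong test.** Section 12.2 itself describes period 1 as randomised by building, so customary two-arm methods could be read to include methods for cluster trials. A MIXED model can also hold a random building effect. This stands. A reader might infer that the sponsor has committed to a person-level analysis, or that the trial's type I error is 10% to 15%. The documents support neither inference. What they show is that the feature deciding whether the tests are valid is left open, and the only cluster named is the person.

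**The inflation may be smaller.** Buildings are paired, and the individual covariates in Section 12.4 may absorb differences in composition. Both points stand. Step 3 covers pairing; the covariate effect cannot be quantified from the documents. The ICCs are described as typical values, not estimates for these outcomes. The planning N of 123 would correspond to an ICC of about 0.0022 ((135/123 − 1)/44) and a size of about 6.1% at 45 per building. The ICCs the plan states are still 0.01 and 0.02, and the mismatch with 123 is a separate issue.

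**Hypothesis 2 may be protected.** A reader might apply 10% to 15% to every Hypothesis 2 contrast. That is not supported: for change from baseline, step 4 runs from no inflation to 18%, depending on assumptions that the documents do not settle.

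**The power figures are not a forecast.** This also stands. The table's differences derive from the pilot's pre-post change with both components delivered together (Sections 2.1 and 2.2), not from a comparison of the two components. If the true difference were half as large (assumption), 4-df power would be about 20% and 17% for plaque and 37% and 30% for gingival.

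**Conclusion.** The point holds as a conditional one. Section 12.4 leaves out how paired, building-level randomisation enters the tests of both main clinical hypotheses. If those tests are run at person level without a building term, an unmatched same-visit comparison has about two to nearly four times the nominal 5% size, using the plan's own ICCs and building sizes (step 2). Pairing, covariate adjustment and stable building effects would each reduce this, in the last case to none for change contrasts, but the plan neither specifies nor guarantees that protection. This should be settled before the primary comparisons are run, because otherwise the choice between a valid and an inflated test can be made after the data are seen.

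**What to change.** In Section 12.4, make the building the unit for between-condition inference and name one primary analysis per hypothesis in advance.

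- **Hypothesis 1.** Use a test on the six building means of the T1 outcome (4 df), preferably using the T0 value already collected. An equivalent mixed model with a random building effect and small-sample degrees of freedom would also serve.
- **Hypothesis 2.** Add a random building effect, and building-by-time where the contrast is of change, with Kenward-Roger degrees of freedom for the T2 and T3 sequence contrasts. If the building variance is estimated as zero, use the building-mean test for that contrast. In simulation this happened in about 40% of trials at ICC 0.01 and 28% at 0.02, so the rule is needed.
- **Pairing.** State in advance whether the paired (2 df) or unpaired (4 df) analysis is primary, and report the other as a sensitivity analysis.
- **Summary of Section 12.4.** Qualify the statement that the planned models are more powerful than the t-tests used for sample size. It need not hold for between-condition contrasts with about 4 df.

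The cost is wording and a small change to the planned SAS code; no new data are needed. The downside to disclose is lower power. The figures in step 5 can illustrate it, provided they carry the caveat about where the pilot differences come from.

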This study will test an intervention designed to change oral health norms and reduce disparities in oral health among vulnerable adults residing in publicly funded senior housing in Central Connecticut. The intervention model is based on Fishbein's modified theory of reasoned action operationalized through Adapted Motivational Interviewing and Practice-to-Mastery (AMI-PM). The intervention includes two components: 1) a face to face administration of the AMI-PM, a participatory counseling model, and 2) a targeted building-level campaign (CA) consisting of up to three half-day oral health events with skills development through practice to mastery (PM) to parallel the individual intervention (CA+PM), all based on the study's conceptual model. The study uses a modified fractional factorial design to evaluate the face to face and campaign components separately and in different additive sequences. Six buildings will be paired in three dyads. The buildings in each dyad will be randomized to either having the AMI-PM intervention first followed by CA+PM or to having the CA+PM first followed by AMI-PM. Sixty residents will be recruited in each building for a total of 360 participants. There will be four assessments:

- 1) To will include a survey, oral hygiene skills assessment and clinical assessment of the Gingival Index and Plaque Score. The survey will provide data on the conceptual domains that are the target of the tailored intervention;
- 2) T1 will follow the AMI-PM or CA+PM (depending on condition) and will include the survey, oral hygiene skills assessment and clinical assessment of the Gingival Index and Plaque Score. This assessment will occur 1-3 months after the AMI-PM or CA+PM;
- 3) T2 will follow the AMI-PM or CA+PM and will include the survey, oral hygiene skills assessment and clinical assessment of the Gingival Index and Plaque Score. This assessment will occur 1-3 months after the AMI-PM or CA+PM.
- 4) T3 will include oral hygiene skills assessment and clinical assessment of the Gingival Index and Plaque Score. This will

occur 16-18 months after study entry. We will use general linear

occur 16-18 months after study entry. We will use general linear mixed models (GLMM) or general estimating equations (GEE), respectively, to fit a model with intervention and period effects using the MIXED procedure in SAS[®].

Objectives: Primary Objectives:

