- 1. To assess the separate and combined effectiveness of two components of a cognitive/behavioral intervention that together improve oral hygiene behaviors and oral hygiene status;
- 2. To assess whether differential sequenced combinations of these components has a differential effect on behavioral and clinical outcomes;
- 3. To investigate the mediation effects of cognitive/behavioral factors in changing clinical outcomes.

Primary Outcome Measures: Plaque Scores and Gingival Index

Secondary Outcome Measure: Oral Health Related Quality of Life

Population: Sample size: 360

Gender: Males and Females

Age: Children and adults aged 18-61 with disabilities and those aged 62 and older who meet income guidelines and may have chronic health conditions with quotas of 52 people 62> and 8 people <61 in cycles II and III established by NIDCR in October, 2016

Demographic group: Vulnerable adults or children; we will recruit from low income senior housing in Central Connecticut. Residents must meet income guidelines and be over the age of 62 or be disabled adults or children.

General health status: The participants are independent living older adults residing in low income senior housing. Residents include vulnerable adults over age 21 and individuals meeting the NIH definition of children ages 18-21.

Geographic location: Central Connecticut

Phase: not applicable

Number of Sites: 6 recruitment sites (housing for seniors and disabled

individuals); The University of Connecticut School of Dental Medicine and the Institute for Community Research are

coordinating sites.

Description of Intervention:

The intervention includes two components: 1) a face to face administration of the AMI-PM, a participatory counseling model, and 2) a targeted building-level campaign consisting of up to three half-day oral health events, all based on the study's conceptual model.

Study Duration: 60 months

Subject
Participation
Duration:

[figure not shown]
16-18 months

Estimated Time to

Complete

Enrollment: approximately 36 months

SCHEMATIC OF STUDY DESIGN:

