12 STATISTICAL CONSIDERATIONS

12.1 Study Hypotheses

- 1. The AMI-PM will produce better short term (T1) clinical outcomes than the Campaign (CA+PM) (AIM 1).
- 2. The CA+PM+AMI-PM will produce better mid-term (T2) and long-term (T3) clinical outcomes than the AMI-PM+CA+PM (AIM 2).
- 3. The AMI-PM will produce more change in mediating cognitive domains than the CA+PM.
- 4. Both AMI-PM+CA+PM and CA+PM+AMI-PM will result in no differences in change in mediating cognitive domains from T0 to T2.
- The greater the dosage (proportion of total talking points recorded for all domains in a tailored AMI; and exposure to campaign activities and messages), the better the outcomes.
- 6. We will investigate an exploratory hypothesis examining the effects of the intervention and sequence on oral health quality of life (a secondary outcome), as well as on clinical outcomes.

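### Hypothesis 2 asks for a sequence difference at T2 and at T3, but the plan names no condition-by-visit term or T2/T3 sequence contrast, so a main-effects fit of its stated model does not answer it

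*Combined protocol and SAP*

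**What the plan says.** Primary objective 2 in the Protocol Summary is "To assess whether differential sequenced combinations of these components has a differential effect on behavioral and clinical outcomes". Section 12.1 turns this into Hypothesis 2: the campaign-first sequence will give "better mid-term (T2) and long-term (T3) clinical outcomes than the AMI-PM+CA+PM (AIM 2"). These are two claims, each tied to a visit.

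Section 12.4 assigns Hypothesis 2 to repeated measures models, under a heading that covers periods 1 and 2. The terms it names are intervention and period: "to fit a model with intervention and period effects using the MIXED procedure". The Précis repeats this: "respectively, to fit a model with intervention and period effects". On correlation, section 12.4 says "Each set of measures from the same person (e.g., gingival outcomes) are treated as a correlated cluster of data" and expects AR-1 to be suitable. On contrasts it says only "Customized contrasts can be constructed to make comparisons" between time points.

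Section 12.2 gives the design two periods. Appendix A puts T3 at 6-7 months after T2, when both components are over, so T3 falls in neither period. Section 5.5.2 mentions a T2 analysis and a T3 analysis of lasting effect, but only to say which withdrawn participants enter each.

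The building is the unit of randomisation. Section 5.4.1: "Buildings will be paired on the basis of their age, ethnicity and gender characteristics and randomized by a statistician". Section 5: "One building in each pair will be randomly assigned to each condition".

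**The concern.** In this design every participant receives both components, so intervention can mean the component just delivered, the assigned arm, or the set of components received so far. These readings lead to different estimates, and the plan chooses none. Without a condition-by-visit term, contrasts between time points in an arm-coded model give only period changes common to both sequences.

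The answer to a primary objective would therefore depend on an undefined word and on which visits enter the model. A T1 difference, which Hypothesis 1 predicts, could be reported as a sequence effect. A real T2 or T3 difference could be diluted. T3 has no stated model at all. In addition, a test that clusters only within person is too liberal when six buildings were randomised.

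**Working it through.** **Plan's own figure.** The last plaque row in section 12.2 has difference 0.20, SD 0.47, 123 per group and two-sided 0.05. Then 0.20 / (0.47 × √(2/123)) = 3.34, and power is Φ(3.34 − 1.96) = 91.6% (91.4% by noncentral t). The plan states 91. This power is for period 1 only; none is stated for Hypothesis 2.

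**Inputs.** SD 0.47 and 123 per group come from section 12.2. The within-person correlation ρ is not given; I assume 0.3, 0.5 and 0.7. D1, D2 and D3 are the true advantage of A:B over B:A at T1, T2 and T3, so negative values favour B:A. The value 0.20 for D1 is the table's pilot pre-post change cut by 25%, so it is an upper-end value for a difference between two active components. I also try 0.10 and 0.05.

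**What each main-effects coding returns.** Under component coding the T1 difference is β and the T2 difference is forced to −β. Least squares gives β = (D1 − D2)/2.

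| Coding of intervention | Visits | Implied T2 difference | T3 |
|---|---|---|---|
| Current component | T1, T2 | (D2 − D1)/2 | not estimated |
| Assigned arm | T1, T2 | (D1 + D2)/2 | not estimated |
| Assigned arm | T0-T3 | weighted average of all visits | same number |
| Received-A and received-B indicators | T1-T2 or T0-T3 | 0 by construction | 0 if included |
| State: A, B, A then B, B then A | T1, T2 | D2 | not estimated |
| State, T3 keeping the T2 state | T0-T3 | one pool of D2 and D3 | same number |

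With AR-1 and equally spaced visits, the arm-coding weights on T0-T3 are 1/(4 − 2ρ) for the two end visits and (1 − ρ)/(4 − 2ρ) for T1 and T2. The weight on T2 is 0.206, 0.167 and 0.115 for ρ = 0.3, 0.5 and 0.7.

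**Leakage when D2 = D3 = 0, no building effect.** Standard errors: component SD√((1 − ρ)/n); arm on T1 and T2 SD√((1 + ρ)/n); arm on T0-T3 SD√(2(1 + ρ)/(n(4 − 2ρ))). For example, component coding at ρ = 0.5 gives SE 0.47 × √(0.5/123) = 0.0300, so 0.10/0.0300 = 3.34 and 91.6% rejection. Each cell gives the estimate, then the rejection rate at ρ = 0.3 / 0.5 / 0.7.

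| D1 | Component, T1-T2 | Arm, T1-T2 | Arm, T0-T3 |
|---|---|---|---|
| 0.20 | −0.10; 80.5 / 91.6 / 99.1% | 0.10; 54.4 / 48.7 / 44.0% | 0.041 / 0.033 / 0.023; 19.9 / 12.3 / 7.6% |
| 0.10 | −0.05; 29.2 / 38.6 / 57.7% | 0.05; 17.9 / 16.1 / 14.8% | 0.021 / 0.017 / 0.012; 8.6 / 6.8 / 5.7% |
| 0.05 | −0.025; 10.9 / 13.3 / 19.0% | 0.025; 8.1 / 7.7 / 7.4% | 0.010 / 0.008 / 0.006; 5.9 / 5.4 / 5.2% |

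The component-coding rates are errors only if that coefficient is reported as the sequence effect. Its spurious sign favours B:A, the direction Hypothesis 2 predicts.

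**Both hypotheses true: D1 = 0.20, D2 = D3 = −0.20.** Arm coding gives 0.00 on T1 and T2 data. On T0-T3 data it gives −0.059, −0.067 and −0.077, rejected about 35% of the time. Component coding gives (−0.20 − 0.20)/2 = −0.20, which is correct, but only because the values are symmetric.

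**State coding with T3 included, D2 = −0.20, D3 = 0.** One pooled estimate of −0.101, −0.105 or −0.121.

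**Buildings.** At ICC 0.01 and 0.02 with 45 per building, the SE of a T2 contrast is √(2 × 0.47² × (1 + 44 × ICC)/135) = 0.0686 and 0.0784. Ignoring buildings it is 0.0572. Using 1.96 × 0.0572 = 0.112 as the critical difference gives type I error of 10.2% and 15.3%.

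**The case against.** The strongest reply is that this is under-specification rather than a wrong model. Section 12.4 does not rule out an interaction, it allows customised contrasts, and section 5.5.2 suggests that analyses by visit were intended. That is fair, and the figures above are conditional on a main-effects fit. But main effects are the only terms the plan names, its contrasts are optional and concern time points, and section 5.5.2 gives no model.

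The size is also assumption-driven. Rejection runs from about 5% to 99% depending on coding, visits, D1 and ρ. The T0-T3 rates assume equal spacing, which Appendix A does not have. Component coding happens to be right in the symmetric case. State coding recovers T2 if T3 is left out. All of this stands. It also shows that the result turns on choices the plan leaves open.

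Finally, building clustering is a separate defect, and the loss of precision comes from that term, not from the visit contrasts. Section 12.4 acknowledges randomisation by site and section 12.2 allows for an ICC. This too is correct. Yet no building effect is specified, and the same model statement has to be rewritten. The 45 per building is the end-of-study number. With all 60 per building, √(2 × 0.47² × (1 + 59 × ICC)/180) × 2.776 still gives a half-width of 0.17 to 0.20.

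**Conclusion.** The concern holds. Hypothesis 2 has no stated estimand at T2 or T3. A main-effects fit of the named terms misses the T2 sequence difference under component or arm coding and gives no separate T3 difference under any coding examined. With a T1 difference of 0.20 and none later, the T1 and T2 fits imply a T2 difference of 0.10 in size, significant in 44% to 99% of trials. At 0.05 the rate is 7% to 19%, and with arm coding on T0-T3 data it is close to nominal. These sizes rest on assumed D1 and ρ, on 123 per group taken at face value, and on no building effect. The algebra for T1 and T2 data does not depend on ρ. The type I error of 10% to 15% from ignoring buildings is additional and rests on the plan's own ICC values.

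Hypothesis 1, the comparison the study is powered on, is analysed separately, and the coding problem does not touch it. The plan should be corrected before analysis.

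**What to change.** In section 12.4 and the matching Précis text, state a model with condition (sequence), categorical visit (T1, T2, T3), condition-by-visit interaction, the baseline value of the outcome and a building effect. Test Hypothesis 2 by the condition contrasts at T2 and at T3.

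State in advance whether the matched pair, which is also the cycle (section 4), is modelled, and fix the degrees of freedom to match: 6 − 2 = 4 without it, 3 − 1 = 2 with it. Without a pair term, the estimated building variance would be zero or negative in 39.9% of trials at ICC 0.01 and 28.0% at 0.02, from F(4, 264). So name a fallback with the same degrees of freedom, such as a t-test on baseline-adjusted building means. In simulation, building-mean tests held the T2 error at 4.4% to 5.4% (4 df) and 4.0% to 4.9% (2 df).

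The change is wording and model statements; no new data are needed. The visit contrasts themselves are a wording change. The building term widens the intervals for the T2 plaque contrast (45 per building, ICC 0.01 to 0.02):

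| | Half-width | Power for 0.20 |
|---|---|---|
| 4 df | 2.776 × SE = 0.19 to 0.22 | 60% to 49% |
| 2 df | 4.303 × SE = 0.30 to 0.34 | 37% to 31% |
| Buildings ignored | 0.11 | not valid |

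These figures are before any variance reduction from pairing or baseline adjustment. Modelling the pair is worthwhile only if it removes enough variance to repay the two degrees of freedom it costs.
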